2.0 Goals

- 2.1 Primary
 - 2.11 Phase I: Determine the maximum tolerated dose (MTD) of lenalidomide in combination with AT-101.
 - 2.12 Phase II: To assess the overall response rate of lenalidomide in combination with AT-101.
- 2.2 Secondary
 - 2.21 To assess the overall response rates of lenalidomide in combination with AT-101 at 6 months and 12 months.
 - 2.22 To evaluate time to progression (TTP) for the combination of lenalidomide + AT-101.
 - 2.23 To evaluate the safety of this combination in patients with relapsed B-CLL.
- 2.3 Correlative Research
 - 2.31 To conduct correlative studies for further understanding of the mechanism of antitumor activity of lenalidomide and lenalidomide + AT-101.

3.0 Patient Eligibility

Phase I only: Prior to discussing protocol entry with the patient, call the MCCC Registration Office () for dose level and to insure that a place on the protocol is open to the patient.

- 3.1 Inclusion Criteria
 - 3.11 Understand and voluntarily sign an informed consent form.
 - 3.12 Age \geq 18 years.
 - 3.13 Able to adhere to the study visit schedule and other protocol requirements.
 - 3.14 Diagnosis of B-CLL, confirmed by flow cytometric analysis and as per the criteria outlined by the IWCLL/Hallek December 2008. (Refer to Appendix III).
 - 3.15 Any prior therapy for B-CLL must have been discontinued \geq 28 days prior to registration.
 - 3.16 Patients must have an absolute lymphocyte count (ALC) of more than 5,000 cell/mm³.
 - 3.17 During Phase I: All patients with relapsed disease will be eligible if they have received at least 1 prior standard CLL therapy^{*} and no more than 4 prior therapies (one of which must be a purine analog and/or an alkylating agent).

During Phase II: All patients with relapsed disease will be eligible if they have received a minimum of 1 prior standard therapy^{*} and a maximum of 2 prior treatments (one of which must be a purine analog and/or an alkylating agent) for B-CLL and have developed relapse disease.

Note: Patients who have refractory disease (defined as – progressive disease on last treatment, or less than 6 months of clinical response to the last treatment) will not be eligible.

* Standard Therapies are defined as those listed in the NCCN guidelines for treatment of CLL.

- 3.18 ECOG performance status of 0, 1 or 2 at registration (see Appendix I).
- 3.19a The following laboratory values obtained \leq 14 days prior to registration:
 - Absolute neutrophil count $\geq 1500/\text{mm}^3$
 - Platelet count \geq 30,000/mm³
 - Serum creatinine $\leq 1.5 \text{ x ULN}$.
 - Total bilirubin $\leq 1.5 \text{ mg/dL}$ or direct bilirubin $\leq 1.0 \text{ mg/dL}$ for patients with Gilbert's syndrome
 - SGOT (AST) and SGPT (ALT) ≤ 2 x ULN or ≤ 5 x ULN if hepatic disease is present.
- 3.19b Females of childbearing potential (FCBP)[†] must have a negative serum or urine pregnancy test with a sensitivity of at least 50 mIU/mL 10 14 days prior to and again within 24 hours before starting lenalidomide and must either commit to continued abstinence from heterosexual intercourse or begin TWO acceptable methods of birth control, one highly effective method and one additional effective method AT THE SAME TIME, at least 28 days before she starts taking lenalidomide. FCBP must also agree to ongoing pregnancy testing. Men must agree to use a latex condom during sexual contact with a FCBP even if they have had a successful vasectomy. All patients must be counseled at a minimum of every 28 days about pregnancy precautions and risks of fetal exposure. See Appendix VI: Risks of Fetal Exposure, Pregnancy Testing Guidelines and Acceptable Birth Control Methods, AND also Appendix VII: Education and Counseling Guidance Document and Appendix VIII: lenalidomide information.

[†] A female of childbearing potential is a sexually mature woman who: 1) has not undergone a hysterectomy or bilateral oophorectomy; or 2) has not been naturally postmenopausal for at least 24 consecutive months (i.e., has had menses at any time in the preceding 24 consecutive months).

- 3.19c All study participants must be registered into the mandatory RevAssist ® program, and be willing and able to comply with the requirements of RevAssist®
- 3.19d Patients must require treatment for symptomatic B-Cell CLL as defined by the IWCLL/Hallek, December 2008 criterion (see Appendix IV) or as determined clinically necessary by the treating physician.

- 3.19e Willing to provide blood and baseline bone marrow aspirate samples for correlative research purposes (see Sections 6.31 and Section 14.0).
- 3.2 Exclusion Criteria
 - 3.21 Any serious medical condition, laboratory abnormality, or psychiatric illness that would prevent the subject from signing the informed consent form.
 - 3.22 Pregnant or lactating females.
 - 3.23 Any condition, including the presence of laboratory abnormalities, which places the subject at unacceptable risk if he/she were to participate in the study or confounds the ability to interpret data from the study.
 - 3.24 Use of any other experimental drug or therapy ≤ 28 days prior to registration.
 - 3.25 Known hypersensitivity to thalidomide or lenalidomide.
 - 3.26 The development of erythema nodosum if characterized by a desquamating rash while taking thalidomide or similar drugs.
 - 3.27 Patients with history of any other cancer (except non-melanoma skin cancer or carcinoma in-situ of the cervix, unless in complete remission and off therapy for that disease for >3 years).
 - 3.28 Patient with history of cardiac arrest within the past 6 months.
 - 3.29a Patients with history of prior bowel resection, malabsorption syndrome, inflammatory bowel disease, prior bowel obstruction (partial or complete), Crohn's disease, or any other disease significantly effecting the gastrointestinal tract.
 - 3.29b Prior use of gossypol or AT-101.

4.0 Test Schedule

| | | Active N | Monitoring | Phase | | |
|---|----------------|---------------------|------------|---------------------------------------|-------------------------------|-----------------------------|
| Tests & Procedures | | Prior to tration | Cycle 1 | Prior to subsequent Cycles 2-12 | Study Drug Discontinuation | Observation |
| | ≤ 28 days | ≤ 14 days | | | 3-4 weeks from the last dose | Every 3 months x 2 years |
| Complete medical history | X | | | | | |
| Adverse event assessment | | Х | | Х | Х | Х |
| Physical exam, including weight and vital signs, and PS ¹ | | X | Х | Х | Х | Х |
| Height | | Х | | | | |
| Tumor measurement by physical exam ^{2, 3} | | X | | Х | Х | Х |
| CT scans (Chest, Abdomen, Pelvis) ⁴ | Х | | | | Х | |
| EKG/ECHO ⁵ | Х | | | | | |
| CBC with differential ⁶ | | X | Х | Х | Х | Х |
| Chemistry group (SGOT [AST], SGPT [ALT], serum creatinine, total bilirubin ¹⁸ , LDH, uric acid, phosphorus, alk phos) ⁶ | | X | Х | Х | Х | Х |
| Quantitative Immunoglobulins | Х | | | Х | Х | Х |
| TSH ⁷ | Х | | | | | |
| Coagulation (PT/PTT) ⁸ | Х | | | Х | | |
| Flow Cytometry- CLL Panel ⁹ | Х | | | Х | Х | Х |
| Bone marrow biopsy and aspirate ¹⁰ | Х | | | Х | Х | Х |
| B-cell gene rearrangement – peripheral ¹¹ | Х | | | | | |
| CLL FISH Panel ¹⁶ , | Х | | | | | |
| Zap 70, CD38, IgHV ¹⁷ | Х | | | | | |
| Urinalysis | Х | | | | | |
| Pregnancy test ¹² | | Х | Х | Х | Х | |
| Beta2 microglobulin | Х | | | | | |
| Research blood sample collection ^{13, R} | | Х | Х | Х | | |
| Research bone marrow aspirate collection ^{14, R} | Х | | Х | Х | Х | |
| Research lymph node aspirate or biopsy collection ^{15, R} | | Х | Х | Х | | |
| T&B cell quantitation ^{13, R} | | Х | Х | Х | | |

- 1. During the first 2 cycles of treatment, patients will have a focused clinical examination weekly for monitoring tumor lysis syndrome (TLS) and tumor flare reaction (TFR). This can be done in collaboration with local MD/referring physician.
- 2. Physical exam should measure the spleen and liver noting the maximal distance below the respective costal margins and should record the bidimensional diameter of the largest palpable node in each area of involvement including the following sites: left neck (sub-mandibular, cervical, supra-clavicular), right neck (sub-mandibular, cervical, supra-clavicular), left axillary, right axillary, left groin (inguinal, femoral) and right groin (inguinal, femoral).
- 3. Response assessment: will be done as per IWCLL criteria starting with evaluation at the end of Cycle 2 and every 2 cycles thereafter during treatment. The response assessment will be done every cycle during observation.
- 4. CT scans should be done as clinically indicated for the management of the patient and in accordance with the IWCLL guidelines. CT scans may be done with patient's primary physician (if outside Mayo Clinic), results of these will be entered in the source document.
- 5. EKG testing must be done as clinically indicated ; ECHO if clinically indicated.
- 6. Hematology (CBC) / Serum Chemistry: During cycle 1 and 2 (day 8 and 15) will be done at the treating physician's' discretion based on patient's clinical needs and/or can be done based on risk for TLS/TFR or for conduct of correlative studies. In subsequent cycles CBC/chemistry will be done prior to beginning of each cycle as standard of care and additional testing will only be done as clinically indicated to be determined by treating physician. Laboratory workup may be done with patient's primary physician (if outside Mayo Clinic), results of these will be entered in the source document.
- 7. TSH level will be done at baseline and subsequent testing will be done as clinically indicated and at the discretion of the treating physician.
- 8. Coagulation testing: Risk assessment for thrombosis may be done at the treating physician's discretion. Patients should receive some form of thromboprophylaxis as recommended in section 9.8 and monitoring will be done as per standard clinical practice.
- 9. Flow Cytometry-CLL Panel: The objective of this is to confirm diagnosis as per standard of care (pretreatment) and during/post treatment to assess minimal residual disease. It may be done every 2 cycles starting with Cycle 3 for patients whose ALC is \leq 5,000 and is not necessary for patients who have persistently elevated ALC (>5,000).
- 10. Bone marrow biopsy / aspirate: at base line will be done to confirm diagnosis, extent of marrow involvement and subsequently will be done only to document complete response as per standard guidelines (see Section 11.0).
- 11. B cell gene rearrangement-Peripheral Blood: to assess B-cell clone (at baseline) as per standard of care and then to assess minimal residual disease (MRD) or recurrence of clone at the discretion of the treating physician.
- 12. Pregnancy test standard recommendation for patients on lenalidomide therapy. Must be done within 10-14 days of initiation of therapy, 24 hours before first dose, weekly for the first 28 days and then every 28 days (or 14 days if menstrual cycles are irregular), and 28 days (or 14 and 28 days if menstrual cycles are irregular) after the last dose of lenalidomide. These are recommended for female patients with child bearing potential. Additional testing is to be done as clinically indicated and at the discretion of the treating physician.
- Blood collected for correlative studies (see Section 14.0) should be collected at baseline; 8 hours, 12 hours and 16 hours post treatment on Cycle 1 Day 1; Cycle 1 Days 8 and 15; Cycle 2 Days 1, 8 and 15; and Cycle 3 Day 1. Samples for the T&B cell quantitation will not be collected after Cycle 2 Day 1.
- 14. Mandatory bone marrow aspirate for correlative studies (see Section 14.0) should be collected at baseline, and optionally at Cycle 2 Day 1, Cycle 6 Day 21, and Cycle 12 Day 21.

- 15. Optional lymph node aspirate or biopsy for correlative studies (see Section 17.0) should be collected as baseline, within 24 hours of tumor flare, 48-72 hours after start of tumor flare, 7-10 days after the start of tumor flare, and at resolution of tumor flare.
- 16. May be performed anytime within the last year.
- 17. Performed at anytime in the past.
- 18. A direct bilirubin should be performed at baseline if the total bilirubin is > 1.5 mg/dL.
- R Research funded.

5.0 Grouping Factor:

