7.12 Phase II

Cycle 1

| Agent | Dose | Route | Day |
|--------------|-----------------------------|-------|------|
| Lenalidomide | MTD per Phase I findings | Oral | 1-21 |

Cycles 2-12

| Agent | Dose | Route | Day |
|--------------|---------------|-------|------|
| Lenalidomide | MTD per Phase | Oral | 1-21 |
| | I findings | | |
| AT-101 | MTD per Phase | Oral | 1-3 |
| | I findings | | |

- 7.2 Phase I determination of Maximum Tolerated Dose (MTD)
 - 7.21 Dose Escalation

| Dose level | Lenalidomide | AT-101 |
|------------|--------------|--------------|
| -2 | 5 mg | 20 mg b.i.d. |
| -1 | 5 mg | 30 mg b.i.d. |
| *1 | 5 mg | 40 mg b.i.d. |
| 2 | 10 mg | 40 mg b.i.d. |
| 3 | 15 mg | 40 mg b.i.d. |
| 4 | 20 mg | 40 mg b.i.d. |

^{*}starting dose level

- 7.211 Treatment by a local medical doctor is not allowed.
- 7.212 Three patients will be treated at each dose level and observed during the first cycle of the combination therapy (i.e., cycle 2: lenalidomide and AT-101, up to day 28 of starting the combination) to assess toxicities, before new patients are treated. Doses will not be escalated in any individual patient.
- 7.213 Investigators are to contact the Study Chair as soon as any dose-limiting toxicity (DLT) occurs.

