7.22 Definitions of DLT

7.221 For this protocol, dose-limiting toxicity (DLT) will be defined as an adverse event at least possibly related to treatment (definitely, probably, or possibly related) that occurs in cycle 2 of the study treatment and meets the following criteria:

| Toxicity | DLT Definition |
|-----------------|--|
| Hematologic | ANC $\leq 0.5 \times 10^{9}$ /L for more than 14 |
| - | days |
| | Febrile neutropenia of any duration |
| | $(ANC < 1.0 \text{ x } 10^{9}/\text{L}, \text{ fever} \ge 38.5^{\circ}\text{C})$ |
| | Grade 4 thrombocytopenia or Grade |
| | 3 thrombocytopenia with bleeding or |
| | any requirement for platelet |
| | transfusion |
| | Grade 4 anemia, unexplained by |
| | underlying disease |
| Non-hematologic | Any grade 3 or 4 (except tumor lysis |
| | syndrome, tumor flare reaction, |
| | fatigue, nausea, hyperglycemia in |
| | diabetic patients) |

| Dose Level | Lenalidomide | AT-101 |
|---------------|--------------|--------------|
| -2 | 5 mg | 20 mg b.i.d. |
| -1 | 5 mg | 30 mg b.i.d. |
| 1* | 5 mg | 40 mg b.i.d. |
| 2 | 10 mg | 40 mg b.i.d. |
| 3 | 15 mg | 40 mg b.i.d. |
| 4 | 20 mg | 40 mg b.i.d. |

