8.2 Lenalidomide

A new course of treatment may begin on the scheduled Day 1 of a new cycle if:

- The ANC is $\geq 1,000/\mu$ L;
- The platelet count is $\geq 25,000/\mu$ L;
- Any lenalidomide-related allergic reaction/hypersensitivity or sinus bradycardia/ other cardiac arrhythmia adverse event that may have occurred has resolved to ≤ grade 1 severity;
- Any other lenalidomide-related adverse event that may have occurred has resolved to \leq grade 2 severity.

If these conditions are not met on Day 1 of a new cycle, the subject will be evaluated weekly and a new cycle of lenalidomide will not be initiated until the toxicity has resolved as described above. If lenalidomide dosing was omitted during the previous cycle and was restarted with a one-level dose reduction without requiring an interruption for the remainder of the cycle, then that reduced dose level will be initiated on Day 1 of the new cycle. If lenalidomide dosing was omitted for the remainder of the previous cycle or if the new cycle is delayed due to toxicity newly encountered on the scheduled Day 1, then the new cycle will be started with a one-level dose reduction.

If either drug is discontinued, patient will come off treatment and go to event monitoring.

| → → Use the NCI Common Terminology Criteria for Adverse Events (CTCAE) version 4.0 unless otherwise specified $\leftarrow \leftarrow$ | | | | |
|---|---|--------------|---|--|
| CTCAE System/Organ/Class (SOC) | ADVERSE EVENT | AGENT | ACTION | |
| | BASED ON INTERVAL | ADVERSE E | EVENTS (Days 2-28) | |
| Investigations | Platelet count decreased*: (Platelets < 10,000/mm ³) | | Omit dose. Follow CBC weekly. If thrombocytopenia resolves to ≤ grade 3 restart lenalidomide at the same dose level. | |
| | | | If thrombocytopenia < 10,000/mm³ recurs, reduce dose by one dose level (5 mg) and continue therapy when platelet count ≥ 25,000/mm³. | |
| | Grade 4 Neutrophil count | | • Omit dose. | |
| | decreased* | | • Follow CBC weekly. | |
| | | Lenalidomide | If neutropenia has resolved to ≤ grade 2, resume dose at same level with GCSF support. | |
| Blood and lymphatic | ≥ Grade 3 Febrile | omi | Omit dose. | |
| system disorders | neutropenia | de | • Follow CBC weekly. | |
| | | | If neutropenia has resolved to ≤ grade 2, resume dose at same level with GCSF support. | |

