Note: Dose modification schedule as outlined in the table above will be applicable to all patients enrolled on the study. This schedule will not be applicable to patients during the two cycles of the combination therapy of the patients enrolled on the phase I portion of the study to clearly define MTD. Once patients on the phase I portion of the study have completed cycle #2 (1st combination cycle) they may be managed based on the dose modification criteria outlined in the table above. Dose modification due to toxicity will be based on dose de-escalation in 5 mg increments from the maximum dose obtained for the individual patient. The optimum dose in any individual patient may be determined by the investigator based on managing toxicity and maximizing response. The maximum dose of lenalidomide permitted will not exceed the MTD determined in the phase I portion of the study and is not to exceed 20 mg daily on days 1 - 21 of a 28 day cycle and the minimum dose permitted is 5 mg daily on days 1 - 21 of a 28 day cycle.

Dose re-escalation: For patients who are dose reduced either for disease or drug related toxicities, lenalidomide dose re-escalation can be considered provided all toxicity has resolved to \leq Grade 1. Patients can be started at minimum of 5mg PO daily on days 1 - 21 of a 28 day cycle and the dose titrated up at 5mg increments weekly to the target dose not to exceed the MTD determined in the phase I portion of the study. The rate of escalation is at the PI discretion based on patient tolerability and concern for tumor lysis syndrome.

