- 15.191 Myelosuppression is dose-dependent and reversible with treatment interruption and/or dose reduction. Monitor CBC w/diff regularly. Instruct patient to report any unusual bruising or bleeding (thrombocytopenia); signs and symptoms of infection (neutropenia); and energy conserving lifestyle (anemia).
- 15.192 Lenalidomide can have thrombotic adverse events (i.e DVT and PE). Instruct patient to report any limb swelling or pain, and to seek medical attention for shortness of breath or chest pain.
- 15.193 Because of the potential for birth defects patients should be instructed in effective methods of birth control. Female patients should use 2 forms of birth control during treatment and for 4 weeks after discontinuing

therapy. Males must be instructed to use a latex condom during any sexual contact with a woman of child bearing potential (even if they have had a vasectomy), because it is unknown if lenalidomide is present in semen.

- 15.194 Patents may experience pruritus, rash and dry skin. Because of the rare risk of Steven's Johnson Syndrome, patients should immediately report any rash to their provider.
- 15.195 Drug may cause hyperglycemia. Patients with diabetes or impaired fasting glucose may need to have their glucose levels monitored more closely.
- 15.196 Gastrointestinal side effects (diarrhea, constipation, nausea, dyspepsia, anorexia, etc) are commonly seen. Manage patient symptomatically and monitor for effectiveness.
- 15.197 Patients may experience myalgias, arthralgias, and other generalized pain. Administer analgesics as ordered and monitor for their effectiveness.
- 15.198 Upper respiratory symptoms (nasopharyngitis, cough, epistaxis, etc.) can be seen. Manage symptomatically and monitor for effectiveness.

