- 16.225 Dose de-escalation: If dose-limiting toxicity meets the stopping boundaries set by the above dose escalation algorithm at dose level 1 (for example, more than 1 out of 3 patients or more than 1 out of 6 patients), the next cohort of three patients will be entered at a dose level of -1. If dose level -1 meets the stopping boundaries, the next cohort of three patients will be entered at dose level -2. Further dose re-escalation will depend on the toxicity profile observed at these dose levels, and reevaluation of the regimen by the study team may be done.
- 16.226 If a patient fails to complete the first 2 cycles of therapy (one cycle of lenalidomide and one cycle of lenalidomide in combination with AT-101) for reasons other than dose-limiting toxicity defined adverse events, the patient will be regarded as uninformative in regard to the primary study goal and an additional patient will be treated at the current dose level; however, all toxicity information will be utilized in the analysis.

16.227 Operating Characteristics for standard cohort of 3 design: The following table gives the probability of dose escalation at a single dose level as a function of the true probability of DLT at that level using the cohorts of 3 design described above.

| True Rate of DLT (%) | Probability of Dose Escalation |
|-------------------------|--------------------------------|
| 10 | 0.91 |
| 20 | 0.71 |
| 30 | 0.49 |
| 40 | 0.31 |
| 50 | 0.17 |

16.23 Analysis Plans: All the relevant results pertaining to toxicity, MTD, response, timed endpoints and laboratory correlates will be examined in an exploratory and hypothesis-generating fashion. The small sample size and the heterogeneous patient population associated with phase I studies restricts the generalizability of the results. Any notable statistical result should only be viewed as preliminary evidence for further study in Phase II trials rather than a definitive finding in and of itself.

16.231 Adverse Events Profile

Platelets and hemoglobin will be graded according to the Grading Scale for Hematologic Adverse Events in CLL Studies in Appendix V. The number and severity of all adverse events (overall and by dose-level) will be tabulated and summarized in this patient population. The Grade 3+ adverse events will also be described and summarized in a similar fashion. This will provide an indication of the level of tolerance for this treatment combination in this patient group.

16.232 Toxicity Profile

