Appendix V Grading Scale for Hematologic Toxicity in CLL Studies

Non Hematologic Toxicity will be scored using NCI CTCAE (version 4.0) for toxicity and adverse event reporting.

Hematologic toxicity will be assessed using IWCLL/Hallek December 2008

Grading scale for hematologic toxicity in CLL studies

| Grade [*] | Decrease in platelets ¹ or Hb ⁺ (nadir) from pretreatment value, % | Absolute neutrophil count/µL ³ (nadir) |
|--------------------|--|--|
| 0 | No change to 10% | ≥ 2000 |
| 1 | 11%-24% | \geq 1500 and < 2000 |
| 2 | 25%-49% | $\geq 1000 \text{ and} < 1500$ |
| 3 | 50%-74% | \geq 500 and < 1000 |
| 4 | $\geq 75\%$ | < 500 |

^{*} Grades: 1, mild; 2, moderate; 3, severe; 4, life-threatening; 5, fatal. Death occurring as a result of toxicity at any level of decrease from pretreatment will be recorded as grade 5.

[†]Platelet counts must be below normal levels for grades 1 to 4. If, at any level of decrease, the platelet count is $< 20 \times 10^{9}/L$ (20 000/µL), this will be considered grade 4 toxicity, unless a severe or life-threatening decrease in the initial platelet count (eg, $20 \times 10^{9}/L$ [20 000/µL]) was present pretreatment, in which case the patient is not evaluable for toxicity referable to platelet counts.

[‡]Hb levels must be below normal levels for grades 1 to 4. Baseline and subsequent Hb determinations must be performed before any given transfusions. The use of erythropoietin is irrelevant for the grading of toxicity but should be documented.

[§]If the absolute neutrophil count (ANC) reaches $< 1 \ge 10^{9}$ /L (1000/µL), it should be judged to be grade 3 toxicity. Other decreases in the white blood cell count, or in circulating neutrophils, are not to be considered because a decrease in the white blood cell count is a desired therapeutic endpoint. A gradual decrease in granulocytes is not a reliable index in CLL for stepwise grading of toxicity. If the ANC was $< 1 \ge 10^{9}$ /L (1000/µL) before therapy, the patient is not evaluable for toxicity referable to the ANC. The use of growth factors such as G-CSF is not relevant to the grading of toxicity, but should be documented.

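### Cycle 2 blood counts are left to discretion, so laboratory-defined DLTs can be missed and the MTD may be set too high

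*Combined protocol and SAP*

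**What the plan says.** **DLT definition and window.** Section 7.221 restricts DLTs to cycle 2, the first cycle of the combination. Section 7.212 sets the observation period as "up to day 28 of starting the combination". The hematologic list includes ANC at or below 0.5 × 10^9/L lasting over 14 days, a platelet item that opens "Grade 4 thrombocytopenia or Grade" and goes on to grade 3 with bleeding or any platelet transfusion, and grade 4 anemia not explained by the disease. Appendix V grades platelets and hemoglobin on the lowest value (its column heading includes "nadir) from pretreatment value").

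**Counts required.** The Test Schedule (4.0) places a CBC before each of cycles 2-12. For the days in between, footnote 6 says: "During cycle 1 and 2 (day 8 and 15) will be done at the treating physician's' discretion based on patient's clinical needs". It adds that the counts can also be done for tumor lysis or flare risk or for the correlative studies. Day 22 is not mentioned.

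**Other references to counts.** Section 8.2 asks for weekly CBCs once a low count has been found. If the start-of-cycle criteria are not met, "the subject will be evaluated weekly and a new cycle of lenalidomide will not be initiated until the toxicity has resolved". A note in 8.2 says of the dose-modification schedule, for phase I: "This schedule will not be applicable to patients during the two cycles of the combination therapy". The nursing guideline in 15.191 says "Monitor CBC w/diff regularly", without an interval.

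**Operating characteristics.** Section 16.227 tabulates "the probability of dose escalation at a single dose level as a function of the true probability of DLT at that level".

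**The concern.** The MTD is the phase I primary endpoint and sets the phase II dose. Lenalidomide is the drug being escalated, and the rationale in Section 1.0 calls its major toxicity hematologic. The events most likely to limit escalation are thus the ones that need a blood count, in a window where the plan only brackets the cycle with counts.

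A site could follow the plan to the letter and record no DLT in a patient who had one. Such an error has one direction: it lowers the recorded DLT rate and makes escalation more likely than 16.227 states. Ascertainment could also vary with the physician's habits.

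Footnote 6 covers chemistry too, so laboratory-defined non-hematologic DLTs may share the gap. That is not pursued here.

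**Working it through.** **1. Can the required counts establish the neutropenia DLT?**

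- The 8.2 start rule needs ANC of at least 1,000/µL on day 1 of a cycle, so the pre-cycle-2 count is not low.
- At most one required count, the one before cycle 3, can then be at or below 500/µL. One low value shows neither onset nor duration.
- To exceed 14 days by day 28, an episode must start by about day 14. Counting both end days, days 14-28 are 15 days and days 15-28 are 14.
- Weekly evaluation after a low pre-cycle-3 count (8.2) could show the duration, but only after day 28. The plan does not say whether those days count.

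**2. Can a nadir be missed?**

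- Entry allows platelets of 30,000/mm³ (3.19a), and a cycle may start at 25,000/µL (8.2). Appendix V makes a count below 20,000/µL grade 4 at any percentage decrease, unless the pretreatment count was already that low.
- A modest, silent fall can therefore be a DLT. If it recovers before cycle 3, no required count records it. The same holds for hemoglobin.
- Still detectable: febrile neutropenia, bleeding, platelet transfusion, clinically evident non-hematologic DLTs, and any cytopenia persisting to the pre-cycle-3 count.

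**3. The plan's own table.** Escalation follows 0/3 DLTs, or 1/3 followed by 0/3. With true DLT rate p and q = 1 − p:

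P(escalate) = q³ + 3pq² × q³ = q³ + 3pq⁵

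At p = 10, 20, 30, 40 and 50% this gives 0.906, 0.709, 0.494, 0.309 and 0.172. Section 16.227 prints 0.91, 0.71, 0.49, 0.31 and 0.17. The table reproduces with p as the true rate, so it assumes every DLT is observed.

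**4. Effect of missed DLTs.** Let f be the share of DLTs that only a blood count reveals, and m the share of those missed. The recorded rate is p(1 − fm). Neither f nor m is in the documents; the values below are assumptions.

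| f, m | 1 − fm | p = 30% | p = 40% | p = 50% |
|---|---|---|---|---|
| none missed | 1 | 0.49 | 0.31 | 0.17 |
| 0.25, 0.10 | 0.975 | 0.51 | 0.33 | 0.19 |
| 0.25, 0.25 | 0.9375 | 0.53 | 0.35 | 0.21 |
| 0.50, 0.25 | 0.875 | 0.57 | 0.40 | 0.25 |
| 0.50, 0.50 | 0.75 | 0.65 | 0.49 | 0.35 |

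Worked cell: p = 40%, f = m = 0.5 gives a recorded rate of 0.40 × 0.75 = 0.30, and 0.7³ + 3(0.3)(0.7⁵) = 0.343 + 0.151 = 0.494.

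**5. Whole design.** The full scheme was simulated: start at level 1, levels −2 to 4, six patients required at the MTD, 60,000 trials per scenario. Assumed true DLT rates were 5, 8, 10, 20, 35 and 50% from level −2 up. The probability that the selected MTD has a true DLT rate of at least 1/3 is:

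- 0.21 with full ascertainment
- 0.25 at (0.25, 0.25)
- 0.30 at (0.5, 0.25)
- 0.40 at (0.5, 0.5)

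On an assumed low-toxicity curve (2, 3, 5, 8, 12, 18%) it is 0 throughout. This is so by construction, because no level reaches 1/3.

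**The case against.** The best defense is that the counts will be done anyway.

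- **Correlative draws.** Footnote 6 names the correlative studies as a reason for a count, and mandatory research blood is drawn on cycle 2 days 8 and 15. But the wording only permits a count. The cycle 2 day 8 and 15 tubes are for molecular targets, and T and B cell quantitation stops at cycle 2 day 1.
- **Grading at each evaluation.** Section 10.6 has platelets and anemia graded at each evaluation, Section 18.1 requires a nadir form at each evaluation, and patients are examined weekly in cycles 1-2. If those weekly visits were evaluations, platelet and hemoglobin values would be needed weekly. But 18.1 refers back to Section 4.0, where adverse event assessment and CBC are set per cycle; the weekly visit is a focused examination for tumor lysis and flare. ANC is not on the 10.6 list.
- **The 8.2 note.** It can be read as suspending dose changes only, and it is inconsistent about whether one or two combination cycles are covered. That criticism stands. The conclusion does not depend on the note, because weekly CBCs in 8.2 begin only after a low count is known.
- **Other safeguards.** Growth factors are barred in cycle 2 because of DLT monitoring (7.11, 9.2), and low-dose warfarin stops at a platelet threshold (9.8). Both presuppose counts; neither sets a testing day. Treatment starts at one site, and phase I treatment by a local doctor is not allowed, which limits variation between physicians.

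What stands is the point about size. Only silent or transient cytopenias are at risk, f and m are not trial data, and with near-complete discretionary testing the effect is negligible.

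**Conclusion.** The concern holds. The schedule does not guarantee that the laboratory-defined hematologic DLTs are seen in the cycle where they count. The neutropenia criterion is the clearest case: the required counts cannot establish it inside the stated window.

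The direction of the error is certain, since missed DLTs can only push escalation above 16.227. Its size is unknown. Over the assumed range, P(escalate) at a true rate of 40% rises from 0.31 to between 0.33 and 0.49. The upper end requires half of all DLTs to be laboratory-only and half of those to be missed. These are scenarios, not estimates. The gap should be closed because it bears on the phase I primary endpoint and costs little to remove.

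**What to change.** Reconcile footnote 6 with 7.221, for phase I patients only:

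1. Make the CBC with differential a required observation on cycle 2 days 8, 15 and 22, in addition to the existing pre-cycle-3 count.
2. State in 7.221 how a duration of over 14 days is determined from weekly counts. Low counts on days 8, 15 and 22 span 22 − 8 = 14 days elapsed, or 15 calendar days if both ends are counted, so the convention decides whether the criterion is met.
3. State whether follow-up counts after day 28 contribute, and how a patient with a missing required count is handled for DLT evaluability.

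The discretionary wording can stay for phase II and other cycles. Weekly counts can still miss a nadir between visits, but they remove most of the gap.

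The cost is one footnote and a short addition to 7.221. Each phase I patient needs a CBC tube at two existing research draws and one draw at an existing weekly visit. With at most 26 phase I patients (16.12), that is no more than 3 × 26 = 78 counts. Footnote 6 already lets laboratory work be done with the primary physician. No dose or treatment rule changes.
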